### **3.6. Cohort 4 (N = 36 [10 initial / 26 expansion] at two times weekly dosing)**

Subjects receive VP-315 via once-daily dosing of 8 mg, administered on 2 consecutive days in one week (W1D1, W1D2). The planned dosing regimen is a split dose of VP-315 for all treatments. The 500 $\mu$ L (8 mg) dose is to be divided into 2 injections given at least 15 minutes and no more than 30 minutes apart, with 30% (150  $\mu$ L) administered in the first injection and the remaining 70% (350  $\mu$ L) with the second injection. Treatment for a second TL may begin on D1 of the next week (W2D1, W2D2). Each individual TL is treated for the assigned 2 days only (regardless of necrosis status). Up to 2 TLs may be treated – up to 4 total doses. Subjects with only 1 TL who complete week one of treatment without complete necrosis receive no additional treatment.

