### **3.7. Cohort 5 (N = 37 [10 initial / 27 expansion] at three times weekly dosing)**

Subjects receive VP-315 via once-daily dosing of 8 mg, administered on 3 consecutive days in one week (W1D1, W1D2, W1D3). The planned dosing regimen is a split dose of VP-315 for all treatments. The 500 $\mu$ L (8 mg) dose is to be divided into 2 injections given at least 15 minutes and no more than 30 minutes apart, with 30% (150  $\mu$ L) administered in the first injection and the remaining 70% (350  $\mu$ L) with the second injection. Treatment for a second TL may begin on D1 of the next week (W2D1, W2D2, W2D3). Each individual TL is treated for the assigned 3 days only (regardless of necrosis status). Up to 2 TLs may be treated – up to 6 total doses. Subjects with only 1 TL who complete week one of treatment without complete necrosis receive no additional treatment.

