### **5.5. Definition of Baseline and Treatment Groups**

Baseline is defined as the most recent non-missing value obtained prior to first injection of study treatment. Summaries will be provided for the following groups, unless limited to a subset of these groups elsewhere in this SAP:

- Part 1
- Part 2
  - Cohort 1
  - Cohort 2
  - Cohort 4
  - Cohort 4 Expansion
  - Cohort 5
  - Cohort 5 Expansion
  - Overall (i.e., Part 2 Total, Displayed Total, or Expansion Total)

No other group or subgroup analyses will be performed.

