### 8.1. Histologic Clearance of Treated Lesions at Excision

Histologic clearance means no residual tumor seen on dermatopathological inspection, i.e., the estimate of viable tumor within estimated volume of the entire tumor bed provided by the dermatopathologist and captured in EDC is zero. When the estimated remaining tumor volume is zero, the histologic diagnosis should be scar.

A summary of histologic clearance will be provided using the histologic diagnosis of excised treated lesions (TL1, TL2) from the end-of-treatment (EOT) visit. The histologic diagnosis categories are as follows:

- Micronodular
- Nodular
- Superficial
- Superficial and Nodular
- Scar

The summary will use the full analysis population, and for each treated lesion, the number and percentage of subjects falling into each histologic diagnosis category will be provided in the summary. The summary will also be run using the per-protocol population as outlined in Section 6 of this SAP.

A separate listing will also be provided for the Excision of all lesions (TL1, TL2, NTL1, NTL2, NTL3) using the enrolled subjects, and this listing will include Lesion Number, Visit, Excision Date, Location, Histologic Diagnosis, Date of Review, Estimate of Remaining Tumor Volume, and Specimen Gross Description.

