### **8.3. Estimate of Remaining Tumor Volume and Reduction in Tumor Volume at Excision**

Protocol endpoints reference that the estimated remaining tumor volume would be necrotic cells:tumor cells. However, estimated remaining tumor volume is the estimated volume of residual viable tumor cells. The assessment in the EDC is expressed as a percentage of viable tumor cells within the tumor bed which is composed of tumor cells (viable and necrotic), fibrosis, and inflammation.

A summary of the estimated remaining tumor volume (0 = None Remaining to 100 = All Remaining) will be provided using descriptive statistics for excised lesions (TL1, TL2, NTL1, NTL2, NTL3) from the end-of-treatment (EOT) visit. A 95% confidence interval for the mean estimated remaining tumor volume will also be provided in the summary using a one sample, two-sided t-test. Summary measures will be repeated for reduction in tumor volume (0 = No reduction to 100 = None Remaining).

The summaries will use the full analysis population, and for each lesion, descriptive statistics will be provided in the summary. The summaries will also be run using the per-protocol population as outlined in Section 6 of this SAP.

A separate listing will be provided for the excision of all lesions as described in Section 8.1 of this SAP.

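### In the smallest groups (Cohort 2, N = 3; Cohort 1, N = 6; sparse TL2 and non-target rows), the t interval for mean remaining tumour volume can cover well below 95%, leave the 0–100 scale, or collapse to zero width

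*SAP*

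**What the plan says.** SAP 8.3 states: "A 95% confidence interval for the mean estimated remaining tumor volume will also be provided", and that it is obtained "using a one sample, two-sided t-test". The scale is given as "0 = None Remaining to 100 = All Remaining". The same summary is then mirrored for reduction in volume, where 100 means nothing is left. Both are produced for the full analysis population and again for the per-protocol population. If EOT values are missing, SAP 8.7 reruns the 8.3 summary with those values filled in.

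SAP 8.1 defines histologic clearance as a lesion whose viable-tumour estimate "provided by the dermatopathologist and captured in EDC is zero". Every cleared lesion therefore sits exactly on the lower bound.

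SAP 5.5 sets the reporting units: "Summaries will be provided for the following groups, unless limited to a subset of these groups elsewhere in this SAP". The list separates Part 1, Cohorts 1 and 2, Cohorts 4 and 5, their two expansion groups, and an overall column. The headings in SAP section 3 give 10 for Part 1, 6 for Cohort 1, 3 for Cohort 2, 10 initial plus 26 expansion for Cohort 4, 10 plus 27 for Cohort 5, and 82 for Part 2 in total. SAP 8 tabulates efficacy by lesion and notes that only TL1 is expected in every subject, so TL2 and NTL1–3 rows can hold fewer values than the cohort N.

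Neither document sets a minimum n, a transformation, bounds on the limits, or an alternative method for small groups.

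**The concern.** A one-sample t interval has its stated level when the data are roughly normal, or when n is large enough for the mean to be. A percentage with a hard floor at 0, and possibly a cluster of values on that floor, is far from normal, and n = 3 or 6 is too small for averaging to repair it. Three things can go wrong: the interval misses the true mean more often than 5% of the time; its limits fall where no value can exist; and if all lesions in a row clear, the SD is 0 and the interval has no width, which presents certainty from three observations.

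What is at stake is how the tables are read. Remaining volume is a secondary efficacy endpoint in Part 2, and the SAP text specifies a confidence interval for no other efficacy endpoint. An interval labelled 95% will be taken at that value when the cohorts are compared informally for later planning.

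**Working it through.** **Inputs from the documents.** Level 95%, two-sided, one-sample t, scale 0–100 (SAP 8.3); clearance equals 0 (SAP 8.1); group sizes 3, 6, 10, 26, 27 and 82 (SAP section 3). Sizes 36 and 37 arise only if initial and expansion subjects are combined. The documents give no distribution for the measure and no expected share of zeros.

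**Step 1: the stated level.** The interval is mean ± t(0.975, n−1) × SD/√n. On simulated normal data (40,000 samples per size) it covers 0.950, 0.951, 0.948, 0.950 and 0.951 at n = 3, 6, 10, 26 and 37. The formula is sound on normal data; the question is the data it will meet here.

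**Step 2: when the lower limit is negative.** This needs no distributional assumption. The lower limit is below 0 when SD/mean exceeds √n / t(0.975, n−1):

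- n = 3: 1.732 / 4.303 = 0.40
- n = 6: 2.449 / 2.571 = 0.95
- n = 10: 3.162 / 2.262 = 1.40
- n = 26: 5.099 / 2.060 = 2.48
- n = 82: 9.055 / 1.990 = 4.55

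At n = 3 a coefficient of variation of only 40% is enough.

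**Step 3: an example at n = 3.** Values 0, 0, 20 give mean 6.67 and SD 11.55. The half-width is 4.303 × 11.55 / 1.732 = 28.7, so the interval is −22.0 to 35.4. Taking reduction as 100 minus remaining, the same lesions give 64.6 to 122.0. Values 0, 0, 0 give 0 to 0.

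**Step 4: probability of a zero-width interval.** With share of zeros p, the chance is p^n. At n = 3: 0.5³ = 12.5% and 0.7³ = 34.3%. At n = 6: 0.5⁶ = 1.6% and 0.7⁶ = 11.8%.

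**Step 5: coverage.** The assumption, which is not from the documents, is a share of zeros from 0 to 70%, with non-zero values drawn from 100 × Beta(1,2); 60,000 samples per setting.

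| n | Coverage, no zeros | Coverage, 50% zeros | Coverage, 70% zeros | Lower limit below 0, 50% zeros | Lower limit below 0, 70% zeros |
|---|---|---|---|---|---|
| 3 | 92% | 79% | 60% | 85% | 65% |
| 6 | 93% | 87% | 76% | 86% | 86% |
| 10 | 94% | 90% | 84% | 52% | 86% |
| 26 | 95% | 93% | 91% | 0.3% | 17% |
| 37 | 95% | 94% | 92% | 0% | 2% |
| 82 | 95% | 94% | 94% | 0% | 0% |

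The 65% at n = 3 is lower than the 85% only because about 34% of those samples are all zeros and give a zero-width interval instead.

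**Step 6: sensitivity to shape.** With 30–70% zeros and non-zero values from Beta(1,3), Beta(2,2) or Beta(3,1.5), coverage is 0.60–0.91 at n = 3, 0.75–0.94 at n = 6, 0.82–0.95 at n = 10, 0.90–0.95 at n = 26–27, and 0.93–0.95 at n = 82. With 0–10% zeros, n = 3 still gives 0.91–0.94. The pattern by group size is the same as in Step 5.

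**The case against.** The strongest reply is that little depends on this interval. SAP 5.2 rules out formal inference, no sample size or decision rule uses the interval, and few readers would lean on a confidence interval from three subjects. The SAP already plans the median, minimum and maximum, a listing of every excised lesion's remaining volume, and counts of lesions diagnosed as scar. That stands, and it limits the point to presentation. It does not justify printing an interval that can be impossible or have no width when the alternative costs almost nothing.

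A second reply is that a large share of zeros is assumed. This is also right. The SAP shows that zeros can occur, not how often, and the non-target lesions are not injected, so there is no basis for assuming many zeros there. But at n = 3 coverage was below 95% in every setting tried, including no zeros at all.

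A reader might go further and infer that the interval is invalid throughout the SAP. The documents do not support that. In the expansion groups and the Part 2 total, coverage is close to nominal, and negative limits are rare except near 70% zeros at n = 26–27.

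It is also tempting to repair the interval with a bootstrap or by cutting it at 0 and 100. Neither restores coverage. A percentile bootstrap covers 88% against 90% for t at n = 10, and 92% against 93% at n = 26 (50% zeros). Truncation leaves coverage unchanged, because the true mean always lies within 0–100.

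**Conclusion.** The point holds for the smallest groups: Cohort 2, Cohort 1, and any TL2 or non-target row with similarly few values. Under the assumed 0–70% zeros with Beta(1,2) non-zero values, coverage is about 60–92% at n = 3 and 76–93% at n = 6. Lower limits are negative in about 65–90% of samples at n = 3. A row with a single value has no interval at all, and the SAP has no rule for that case. At n = 10 (Part 1 and the two initial groups) the answer depends on the share of zeros, with coverage from 84% to 94%. At n = 26 and above the t interval is acceptable for a descriptive table.

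Two parts of the argument need no assumption: the threshold for a negative limit in Step 2, and the collapse to zero width when all lesions clear. The size of the coverage loss is conditional on the assumed distribution. No conclusion of the trial is formally at risk.

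**What to change.** In SAP 8.3:

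- State a minimum number of non-missing lesion values for the t interval of the mean, applied to each lesion row. It should at least exclude the n = 3 and n = 6 groups and rows of similar size. The documents offer no basis for one exact cutoff, and whether n = 10 qualifies is a judgement the sponsor should make and record.
- Below the minimum, show the individual values with median and range, for both remaining volume and reduction.
- Keep the t interval for the larger and pooled groups.
- Add an exact Clopper-Pearson 95% interval for the proportion of lesions with zero viable tumour, in every group. It guarantees at least its stated coverage at any n and matches the clearance definition in SAP 8.1. Examples: 2 of 3 gives 9% to 99%; 5 of 10 gives 19% to 81%; 13 of 26 gives 30% to 70%. If 3 of 3 clear, the lower limit is 0.025^(1/3) = 29%, where the t interval for the mean would have no width.

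The cost is a few sentences and minor programming, and the smallest groups lose an interval for the mean. If the database is already locked, SAP 5.2 would require the added interval to be labelled post hoc.

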## 2. Objectives and Endpoints

The following objectives and endpoints will be considered.

Part 1	
Primary Objectives	Endpoints

 
To assess the safety, tolerability, and maximum tolerated dose (MTD) of ascending dose strengths of VP-315
 
	
 
Discontinuations due to adverse events (AEs); occurrence of dose-limiting toxicities (DLTs)
 
Cutaneous Reaction Assessment (CRA)
 

Exploratory Objectives 
 
To evaluate the objective antitumor efficacy of VP-315
 
	
 
Histological clearance of treated lesion(s) at excision
 
Clinical clearance of treated lesion(s) as determined by visual assessment (no tumor seen upon visible inspection) at excision
 
Estimate of remaining tumor volume (necrotic cells:tumor cells) at excision
 
Estimate of reduction in tumor volume (necrotic cells:tumor cells) at excision*
 
Abscopal effect as determined by
 

	
clinical and histological clearance of nontreated lesions at excision
 
 
• Physician Global Assessment (PGA)
 

Part 2 (Cohorts 1 and 2)	
Primary Objectives	Endpoints

 
• To determine the optimal regimen for dosing 8 mg of VP-315 based on safety and tolerability
 
	
 
• Treatment-related AEs; treatment-related serious adverse events (SAEs); discontinuations due to AEs; occurrence of TRAEs of special interest
 
• CRA
 

Secondary Objectives	Endpoints

 
• To evaluate the antitumor efficacy of VP- 315
 
	
 
• Clinical clearance of treated lesion at excision as determined by visual assessment (no residual tumor seen on visual inspection)
 
• Histological clearance of treated lesion(s) at excision
 
• Abscopal effect as determined by clinical and histological clearance of nontreated lesions at excision if nontreated lesions exist
 
• Estimate of remaining tumor volume (necrotic cells:tumor cells) at excision
 
• Estimate of reduction in tumor volume (necrotic cells:tumor cells) at excision*
 
• PGA
 

Exploratory Objectives	Endpoints

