
 
• To assess the immune response to VP-315 treatment in a subset of subjects by assessing the immune repertoire in blood and in tissue
 
	
 
• Multiplex immunohistochemical staining for T-cell subsets and immune activation markers in tumor tissue samples
 
• Analysis of T-cell clonality in blood and tumor tissue samples
 

 
• To assess subject satisfaction with the treatment
 
	
 
• SCAR-Q, FACE-Q
 

Part 2 (Cohorts 4 and 5)	
Primary Objectives	Endpoints

 
• To gain additional information on the
 
	
 
• Treatment-related AEs; treatment-
 

Verrica Pharmaceuticals Inc.  
Protocol: VP-315-201

Statistical Analysis Plan  
6-Sep-2024

safety, tolerability, and dosing regimen of VP-315 to support a pivotal study protocol design	related serious adverse events (SAEs); discontinuations due to AEs; occurrence of TRAEs of special interest 
 
● CRA
 

Secondary Objectives	Endpoints

 
● To confirm the antitumor efficacy of VP-315 using the optimal dosing regimen determined in Part 2
 
	
 
● Clinical clearance of treated lesion at excision as determined by visual assessment (no residual tumor seen on visual inspection)
 
● Histological clearance of treated lesion(s) at excision
 
● Abscopal effect as determined by clinical and histological clearance of nontreated lesions at excision if nontreated lesions exist
 
● Estimate of remaining tumor volume (necrotic cells:tumor cells) at excision
 
● Estimate of reduction in tumor volume (necrotic cells:tumor cells) at excision*
 
● PGA
 

 
● To characterize the pharmacokinetics (PK) of an 8 mg dose of VP-315 administered with the optimal dosing regimen determined in Part 2.
 
	
 
● Plasma VP-315 concentrations
 

Exploratory Objectives	Endpoints

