### 7.3. Demographics and Baseline Characteristics

A summary of Demographics and Baseline Characteristics will be provided for enrolled subjects and for the analysis populations listed in Section 6 of this SAP. Baseline values will be used in summaries of parameters collected at multiple visits.

Descriptive statistics will be provided for the following parameters:

- Age (years),
- Height (cm),
- Weight (kg),
- Body Mass Index (BMI) (kg/m^2),
- Serum Tryptase (ug/L),
- Total Number of Clinically Diagnosed BCC Lesions where a Clinically Diagnosed BCC Lesion means any reported lesion with a non-missing date of clinical diagnosis of BCC,
- Total Number of Pathology Diagnosed BCC Lesions where a Pathology Diagnosed BCC Lesion means any reported lesion with a non-missing date of dermatopathology diagnosis of BCC,
- Smallest Lesion Diameter Before Biopsy (cm),
- Largest Lesion Diameter Before Biopsy (cm), and
- Duration of Disease (months) where Duration of Disease = (Treatment Start Date – Earliest Date of Dermatopathology Diagnosis of BCC) / 30.4375.

The number and percentage of subjects will be provided for the following parameters:

- Sex (Male, Female),
- Female Childbearing Potential (Yes, No),
- Race (American Indian or Alaska Native, Asian, Black or African American, Native Hawaiian or Other Pacific Islander, White, Mixed Race, Unknown or Not Reported),
- Ethnicity (Hispanic, Not Hispanic, Unknown or Not Reported),
- Fitzpatrick Skin Type (I-VI),
- Histologic Diagnosis at Screening (Micronodular, Nodular, Superficial) for TL1, TL2, NTL1, NTL2, NTL3, and

- BCC Location at Screening (Face or Neck, Clavicle or Shoulder, Arm, Chest or Abdomen, Back, Buttocks or Groin, Leg or Foot) for TL1, TL2, NTL1, NTL2, NTL3.

Separate listings using enrolled subjects will be provided for the following:

- Demographics and Baseline Characteristics (Age, Sex, Female Childbearing Potential, Race, Ethnicity, Height, Weight, BMI, Fitzpatrick Skin Type, Duration of Disease),
- Screening Clinical Evaluation (Lesion Number, Lesion Diameter (cm), Location, Date of Clinical Diagnosis, Date of Dermatopathology Diagnosis, Histologic Diagnosis),
- Screening Biopsy (Lesion Number, Biopsy Performed (Yes, No), Visit, Biopsy Date, Timing of Biopsy (Historical, At screening), Biopsy Type (Punch, Shave), Size of Punch Biopsy (2mm, 3mm, Other), Biopsy Sutures Removed (Yes, No), Date Biopsy Sutures Removed), and

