- Biopsy Results (Lesion Number, Visit, Biopsy Date, Biopsy Type (Punch, Shave), Location, Date of Review, Histologic Diagnosis, Specimen Gross Description).

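### SAP 8.3's 'reduction in tumor volume' is the complement of a single excision reading, not a measured change, and it carries a ratio label that the recorded value cannot supply

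*SAP*

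**What the plan says.** SAP 8.3 states what is recorded. The estimate at excision is held in EDC as a "percentage of viable tumor cells within the tumor bed which is composed of tumor cells (viable and necrotic), fibrosis, and inflammation". The main summary uses that value directly: "A summary of the estimated remaining tumor volume (0 = None Remaining to 100 = All Remaining) will be provided". It covers TL1, TL2 and NTL1 to NTL3 at the end-of-treatment visit, with a 95% t interval for the mean. The next step is the one at issue: "Summary measures will be repeated for reduction in tumor volume (0 = No reduction to 100 = None Remaining"). No formula for reduction appears in SAP 2, 8.3 or 14.

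The excision listing in SAP 8.1 holds the only planned viable-tumor estimate: "this listing will include Lesion Number, Visit, Excision Date, Location, Histologic Diagnosis, Date of Review, Estimate of Remaining Tumor Volume, and Specimen Gross Description". The screening listings in SAP 7.3 hold none: "Screening Clinical Evaluation (Lesion Number, Lesion Diameter (cm), Location, Date of Clinical Diagnosis, Date of Dermatopathology Diagnosis, Histologic Diagnosis") and "Biopsy Results (Lesion Number, Visit, Biopsy Date, Biopsy Type (Punch, Shave), Location, Date of Review, Histologic Diagnosis, Specimen Gross Description").

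SAP 2 names two endpoints, "Estimate of remaining tumor volume (necrotic cells:tumor cells) at excision" and "Estimate of reduction in tumor volume (necrotic cells:tumor cells) at excision". Each appears three times: for Part 1, for Part 2 Cohorts 1 and 2, and for Part 2 Cohorts 4 and 5. The second is marked as an addition to the protocol. The first item of SAP 14 repeats the ratio for reduction. The third item of SAP 14, like SAP 8.3, replaces the ratio with percent viable tumor in the bed, but only for remaining volume.

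**The concern.** A reduction is a comparison of two states, and the plan observes one. A reader of the tables would take the mean reduction as the average shrinkage from before treatment. What will be tabulated is the non-viable share of the bed at excision. The same applies to the uninjected lesions NTL1 to NTL3: any whose bed is less than 100% viable tumor will show a positive reduction, whether or not anything changed.

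The label is a second problem. SAP 8.3 sets aside the necrotic-to-tumor-cell ratio as a description of remaining volume, yet SAP 2 and SAP 14 attach that ratio to the endpoint the SAP itself created. SAP 13 ranks the SAP above the protocol, which does not settle a conflict inside the SAP.

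The study has no formal inference, so the names of the summaries carry the message. Both endpoints are secondary in Part 2, where Cohorts 4 and 5 are meant to inform a pivotal design.

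**Working it through.** The plan gives no figure to reproduce here. The check asks what the anchors imply, when the result is a reduction, and whether the label fits.

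**Inputs**
- R = recorded percent viable tumor in the bed at excision (SAP 8.3).
- v = percent of the bed that was viable before treatment. Neither document gives it; 40 to 100 is assumed for illustration.
- The bed is taken to be the same size before and after (also an assumption).

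**1. Implied formula.** R = 0 is none remaining on one scale and must be 100 on the other. R = 100 is all remaining and must be 0. Reversing a 0 to 100 scale gives reduction = 100 − R.

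**2. Does it add information?** No. For readings 0, 0, 50:
- remaining: mean 16.7, SD 28.9
- reduction: mean 100 − 16.7 = 83.3, SD 28.9

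For ten assumed readings (0, 0, 0, 0, 5, 10, 20, 30, 40, 50), the mean of 15.5 (95% CI 2.2 to 28.8) becomes 84.5 (71.2 to 97.8). The interval is reflected.

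**3. When is it a reduction?** The relative loss of viable tumor is 100(v − R)/v. The complement exceeds it by (100 − R) − 100(v − R)/v = R(100 − v)/v. This is zero only if v = 100 or R = 0.

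| Assumed v | Complement at R = 20 | Relative loss at R = 20 | Complement if lesion unchanged (R = v) |
|---|---|---|---|
| 100 | 80 | 80.0 | 0 |
| 80 | 80 | 75.0 | 20 |
| 60 | 80 | 66.7 | 40 |
| 40 | 80 | 50.0 | 60 |

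At R = 0 the complement is 100 and the relative loss is 100% at any v, so cleared lesions are scored correctly. If the bed changed size, the direction of the difference would not be fixed either.

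**4. Does the label fit?** The SAP does not say whether the second term of the ratio is all tumor cells or viable ones, so both are shown. In every row R = 20 and reduction = 80.

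| Viable, % of bed | Necrotic, % of bed | Necrotic / all tumor cells | Necrotic / viable |
|---|---|---|---|
| 20 | 0 | 0 | 0 |
| 20 | 20 | 20/40 = 0.50 | 1 |
| 20 | 40 | 40/60 = 0.67 | 2 |
| 20 | 80 | 80/100 = 0.80 | 4 |

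One recorded value fits many ratios, so the ratio cannot be recovered on either reading. Necrotic/viable is also undefined whenever R = 0.

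**5. Label count.** Reduction carries the ratio 3 times in SAP 2 and once in SAP 14 (4). Remaining volume carries it 3 times in SAP 2. Total 4 + 3 = 7.

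**The case against.** Four points can fairly be made for the plan.

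- **The derivation is plain.** The anchors are reversed on one scale, and a programmer would compute 100 − R. This stands. A reader might infer that the endpoint cannot be programmed, and that would be wrong. The fault lies in what the name claims.
- **The bed may stand for the tumor's former extent.** The denominator is the whole bed, so the specimen could serve as its own reference. The documents do not exclude this reading, so the defect is an unstated assumption, not proof of a wrong measure. The assumption still has to be written down.
- **The ratio is already overridden for remaining volume.** SAP 8.3 and the third item of SAP 14 do this, so the three leftover labels in SAP 2 are unlikely to mislead an analyst. This also stands. It does not cover the four labels on reduction.
- **The consequence is limited.** There is no inference, no decision rule uses the measure, and remaining volume is shown for the same lesions. The formal abscopal summary (SAP 8.4) uses clearance, not this measure.

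A reader might also want to put a number on the overstatement, by assuming a viable share for an untreated bed or by treating the screening biopsy site as tumor-free bed. The documents support neither. They give no viable share and do not say how a healed biopsy site is counted. The table in the working shows what is possible, not how large the effect is.

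**Conclusion.** The point holds as a naming and definition fault. Under the plan, the complement of one excision percentage will be reported as a reduction, for treated and untreated lesions. For a bed of fixed extent with some viable tumor left, it equals a reduction only if the whole bed was viable tumor before treatment. The documents neither state nor measure that, so any offset cannot be sized from them. The ratio label on this endpoint, four times, describes a quantity that the recorded value does not determine. The three labels on remaining volume are a lesser, tidying matter.

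A reader might infer that the efficacy results as a whole are in doubt. They are not. Histologic clearance depends only on a recorded value of zero, and remaining volume keeps its meaning as defined in SAP 8.3. The matter should be corrected because the SAP contradicts itself and the remedy is nearly free. It does not threaten the study.

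**What to change.** 1. Drop the reduction measure, which adds nothing to remaining volume. Alternatively, rename it 'percentage of tumor bed without viable tumor at excision' and define it in SAP 8.3 as 100 minus the recorded value.
2. If it is kept, footnote each table to say that no pre-treatment value enters the measure and that it is not a measured change from baseline. Carry the same wording into the SAP 8.7 rerun if the measure is shown there.
3. Remove the necrotic-to-tumor-cell ratio from reduction in SAP 2 (three places) and in the first item of SAP 14.
4. Align the remaining-volume label in SAP 2 (three places) with the definition in SAP 8.3.

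The cost is SAP wording, table titles and footnotes. No new data or assessments are needed. The downside is a less striking endpoint name.
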